9.10. Dose Reduction/Interruption/Delay

For CC-122, dose reduction is defined as a decrease in dose (non-zero) between current and the immediately previous non-missing assigned dose (planned cohort dose level if the first dose) or between assigned dose and actual dose. Total days of dose reduction due to AE include all the days from the start of assigned dose decrease due to AE until either the assigned dose is changed (excluding missing values) or a new (non-missing) reason for assigned dose adjustment is entered, including the days with dose not administered, as well as those days when the actual dose administered is less than the assigned dose due to AE (count only once if redundant with the previous interval). Dose interruption occurs if the dose is not administered except as pre-specified by the protocol (i.e. rest period). If an interruption happens at the start of a cycle and causes a cycle to be postponed, it is also called dose delay. Consecutive doses not administered (including those separated by protocol planned rest period) with the same reason are counted as one interruption. The rest period between two consecutive dose interruptions due to AE will be included in the total days for that dose interruption.

For Nivolumab, a skipped infusion is defined as an infusion that is not administered at all before the subject discontinues from Nivolumab treatment. An incomplete infusion is defined as an infusion for which the actual dose administered is less than the dose assigned.

Dose reduction and interruption will be summarized and summaries will include:

For CC-122

- Frequency count of number of dose reductions;
- Frequency count of number of dose interruptions;
- Reason for dose reduction (including the reason for assigned dose adjustment and the reason for actual dose that is different from assigned dose);
- Reason for dose interruptions;
- Descriptive statistics of time to the first dose reduction (from the first dose);
- Descriptive statistics of time to the first dose reduction (from the first dose) due to an adverse event (AE) for those who have at least one dose reduction due to an AE;
- Descriptive statistics of time to the first dose interruption (from the first dose);

- Descriptive statistics of time to the first dose interruption (from the first dose) due to an AE for those who have at least one dose interruption due to an AE;
- Number and percentage of subjects who have ≥ 7 days of dose interruption due to an AE;
- Descriptive statistics of total days of dose reduction due to an AE for those who have at least one dose reduction due to an AE;
- Descriptive statistics of total days of dose interruption due to an AE for those who have at least one dose interruption due to an AE.

For Nivolumab

- Number of incomplete infusions;
- Number of skipped infusions;
- Reason for incomplete infusion;
- Reason for skipped infusion;
- Descriptive statistics of time to the first incomplete infusion (from the first dose);
- Descriptive statistics of time to the first incomplete infusion (from the first dose) due to an adverse event (AE) for those who have at least one dose reduction due to an AE;
- Descriptive statistics of time to the first skipped infusion (from the first dose);
- Descriptive statistics of time to the first skipped infusion (from the first dose) due to an AE for those who have at least one dose interruption due to an AE.

10. EFFICACY ANALYSIS

The efficacy endpoints of this study include ORR, DCR, DoR, PFS, TTP and OS. Tumor response and progression will be determined by the Investigator based on RECIST 1.1 () as a primary guideline, and irRECIST () as an exploratory assessment.

Tumor assessments will be performed at screening (up to 28 days before the Cycle 1 Day 1 [C1D1] dose), every 8 weeks (\pm 7 days) for the first 5 evaluations (10 months) and thereafter every 12 weeks (\pm 7 days), regardless of treatment status. Tumor assessments should also be performed at any time, if clinically indicated. Tumor assessments should continue at the defined schedule until radiologic disease progression or new anticancer therapy, beyond the end of treatment if necessary.

Following disease progression, survival status will be determined approximately every 3 months thereafter until 2 years from enrollment, lost to follow-up, death or withdrawal of consent, whichever occurs sooner.

Survival follow-up may be conducted by record review (including public records) and/or telephone contact with the subject, family, or the subject's treating physician.

All summaries, analyses and figures of efficacy data will be presented as applicable by dose cohorts in dose escalation part, by selected subgroups in dose expansion part, by selected subgroup at the expanded dose with subjects from both parts, unless otherwise specified.

Individual listings of tumor assessment and derived endpoints will be provided, which include:

- For RECIST 1.1 and irRECIST, listing for total measured tumor burden (TMTB), including change (in mm and percentage) from baseline and change from nadir for each visit; the TMTB is calculated separately for target and new measurable lesions as the sums of the respective diameters of target and new measurable lesions; nadir is the smallest TMTB of all assessments since study treatment starts before the current assessment.
- Listing for non-target lesions (RECIST 1.1) and new non-measurable lesions (irRECIST);
- Listing of overall response by visit unconfirmed and confirmed best overall response (BOR) using RECIST 1.1;
- Listing of unconfirmed BOR using irRECIST;
- Listing of DoR, duration of Stable Disease (SD) and time to BOR (using RECIST 1.1);
- Listing of PFS, TTP (using RECIST 1.1) and OS with flags for the censored data;
- Listing of DoR, duration of Stable Disease (SD) and time to BOR (using irRECIST);
- Listing of PFS and TTP (using irRECIST) with flags for the censored data;

The detailed rules for using dates are described in Section 17.2.1.

10.1. Response Criteria

Investigators will use RECIST 1.1 and irRECIST to assess tumor response for subjects treated with CC-122 in combination with Nivolumab (see Table 4).

Table 4: Time Point Overall Tumor Response Definitions by RECIST 1.1 and irRECIST

Overall Response RECIST 1.1	RECIST 1.1 ^[1]	Overall Response irRECIST	irRECIST ^[2]
CR	Disappearance of all target lesions, disappearance of all non-target lesions and normalisation of tumor marker level. All lymph nodes must be non-pathological in size (<10mm short axis).	irCR	Complete disappearance of all measurable and non-measurable lesions. Lymph nodes must decrease to < 10 mm in short axis. Confirmation of response is not mandatory.
PR	At least a 30% decrease in the sum of diameters of target lesions, taking as reference the baseline sum diameters, no unequivocal progression of non-target lesions and no new lesion(s), but the criteria for CR are not met	irPR	Decrease of $\geq 30\%$ in TMTB relative to baseline, non-target lesions are irNN, and no unequivocal progression of new non-measurable lesions.
SD	Neither sufficient shrinkage in the sum of diameters of target lesions to qualify for PR nor sufficient increase to qualify for PD, taking as reference the smallest sum diameters while on study, no unequivocal progression of non-target lesions and no new lesion(s).	irSD	Failure to meet criteria for irCR or irPR in the absence of irPD.
PD	At least a 20% increase in the sum of diameters of target lesions from nadir. In addition, the sum must also demonstrate an absolute increase of at least 5 mm, or unequivocal progression of non-target lesions, or appearance of new lesion(s).	irPD	At least 20% increase and minimum 5 mm absolute increase in TMTB compared to nadir, or irPD for non-target or new non-measurable lesions. Confirmation of progression is recommended minimum 4 weeks after the first irPD assessment.

Abbreviations: CR = Complete Response; PR = Partial Response; SD = Stable Disease; PD = Progressive Disease; ir=immune-related; irNN = irNon-CR/Non-PD, TMTB = total measured tumor burden,

^[1] RECIST 1.1 overall response is based on the sum of diameters of the target lesions.

^[2] irRECIST overall response is based on TMTB for target and new measurable lesions.

Table 5: RECIST 1.1 Best Overall Response When Confirmation of CR and PR is Required

Overall Response First Time Point	Overall Response Subsequent Time Point	Best Overall Response
CR	CR	CR
CR	PR	SD, PD or PR ^[1]
CR	SD	SD provided minimum criteria for SD duration met, otherwise, PD
CR	PD	SD provided minimum criteria for SD duration met, otherwise, PD
CR	NE	SD provided minimum criteria for SD duration met, otherwise NE
PR	CR	PR
PR	PR	PR
PR	SD	SD
PR	PD	SD provided minimum criteria for SD duration met, otherwise, PD
PR	NE	SD provided minimum criteria for SD duration met, otherwise NE
NE	NE	NE

Abbreviations: CR = complete response, PR = partial response, SD = stable disease, PD = progressive disease, NE = non evaluable.

[1] If a CR is truly met at first time point, then any disease seen at a subsequent time point, even disease meeting PR criteria relative to baseline, makes the disease PD at that point (since disease must have reappeared after CR). Best response would depend on whether minimum duration for SD was met. However, sometimes 'CR' may be claimed when subsequent scans suggest small lesions were likely still present and in fact the subject had PR, not CR at the first time point. Under these circumstances, the original CR should be changed to PR and the best response is PR.

Note: All responses after first PD will not be considered as a response.

10.2. Best Overall Response (BOR)

Confirmed and unconfirmed BOR (or irBOR) will be summarized using frequency tabulation for the Safety Population and EE Population, separately.

Confirmed BOR will only be used to summarize ORR by RECIST1.1, with unconfirmed BOR used in the derivation of ORR, DCR, sustained DCR, DoR, duration of SD, PFS and TTP.

Unconfirmed BOR will be used for graphs.

Figures of tumor assessment will be provided, which include:

- Waterfall plots: Each subject's best percent change as defined below will be represented by a bar, with a pattern specific to the dose cohort to which they were initially assigned to (in the dose escalation part) and designated subgroup (in dose expansion part), and with their overall relative dose intensity annotated below/above each bar. For each study phase, a separate graph on the next page will be produced.
 - For RECIST 1.1, a waterfall plot of best percentage change from baseline in the sum of diameters (longest for non-nodal lesions, short axis for nodal lesions) of target lesions for all subjects with non-missing target lesion.
 - For irRECIST, waterfall plot for best percent change from baseline in TMTB, for all subjects with non-missing TMTB.
- Spider plots: Each subject's percent change from baseline as defined below, will be represented by lines with a colour specific to the dose cohort to which they were initially assigned to (in the dose escalation part) and designated subgroup (in dose expansion part). For each phase, a separate graph on the next page will be produced.
 - For RECIST 1.1, a spider plot of percent change from baseline in target lesions by time from first dose.
 - For irRECIST, a spider plot of percent change from baseline in TMTB by time from first dose

Unconfirmed BOR - RECIST 1.1

Unconfirmed BOR is the best of overall response across all time points evaluated by investigator using RECIST 1.1 criteria as defined in [Table 4](#). The order in which responses are rated are CR, PR, SD, Progressive Disease (PD), not evaluable (NE). BOR is derived from post-baseline responses up until the date of progression or data cut-off date if progression has not occurred prior to the cut-off date. For example, if a subject has overall responses of PR, SD and PD, the unconfirmed BOR would be PR.

Duration of SD must meet minimum duration for at least 6 weeks if the BOR is SD. If the minimum time for a best response of SD is not met, the subject's best response depends on the subsequent assessments.

For example:

- A subject who has SD at the first assessment, PD at the second but does not meet minimum duration for SD, will have a best response of PD. PD assessment does not

required to be confirmed. A subject who has SD at the first assessment and is then lost to follow-up would be considered not evaluable.

Confirmed BOR – RECIST 1.1

Confirmed BOR is derived using Table 5 to confirm the best response. Confirmation of response requires repeat assessment of response (CR or PR) at the next scheduled scan more than 4 weeks following the first assessment meeting response criteria. If best overall response is SD, it must meet the minimum duration of 6 weeks. If the minimum time for a best response of SD is not met, the subject's best response depends on the subsequent assessments.

irBOR – irRECIST

In irRECIST, the determination of the adaptation of the immune-related unconfirmed best overall response (irBOR) is the single best immune-related response of overall response across all time points (post-baseline) evaluated by investigator using irRECIST criteria defined in Table 4. The order in which responses are rated are irCR, irPR, irSD, irPD, irNE. For example if a subject has overall responses of irPR, irSD and irCR, the unconfirmed irBOR would be irCR. The same minimum duration of SD required in RECIST 1.1 must be met if the best overall response is irSD.

Objective Response Rate (ORR) and Disease Control Rate (DCR)

Unconfirmed ORR, confirmed ORR, DCR and sustained DCR will be derived separately for investigator RECIST 1.1 and irRECIST assessment [REDACTED]

Table 6: ORR and DCR Derivation rules

Endpoint	Confirmed	Criteria	Derivation
ORR	Yes	RECIST 1.1	Confirmed BOR of CR or PR
	No	RECIST 1.1	Unconfirmed BOR of CR or PR
	No	irRECIST	Unconfirmed irBOR of CR or PR
DCR	No	RECIST 1.1	Unconfirmed BOR of CR, PR or SD
	No	irRECIST	Unconfirmed irBOR of CR, PR or SD
Sustained DCR	No	RECIST 1.1	Unconfirmed BOR of CR, PR or SD (duration of SD \geq 16 weeks)
	No	irRECIST	Unconfirmed irBOR of CR, PR or SD (duration of SD \geq 16 weeks)

Abbreviations: BOR = best overall response; CR = complete response, SD = stable disease, PR = partial response, ir = immune related

Note: the immune-related endpoints will be referred to as irORR, irDCR and sustained irDCR respectively.

Frequency count and percentage of subjects meeting the criteria of each of the endpoints defined in [REDACTED] will be provided. In addition, two-sided 95% Clopper-Pearson ([REDACTED]) exact CIs will be provided for each endpoint. The summaries and inferential statistics will be provided for the Safety Population and EE Population.

In dose expansion phase, a figure (similar to a forest plot) of the estimate and associated two-sided Clopper-Pearson ([REDACTED]) 95% CI will be provided for each endpoint defined in [REDACTED] using the Safety Population for selected subgroups. The figures will also be provided for the EE Population.

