10.2.1.	Seriousness	80
10.2.2.	Severity / Intensity.....	82
10.2.3.	Causality	82
10.2.4.	Duration	83
10.2.5.	Action Taken	83
10.2.6.	Outcome.....	83
10.3.	Abnormal Laboratory Values.....	83
10.4.	Pregnancy.....	83
10.4.1.	Females of Childbearing Potential	84
10.4.2.	Male Subjects	84
10.5.	Reporting of Serious Adverse Events.....	85
10.5.1.	Safety Queries	85
10.6.	Expedited Reporting of Adverse Events.....	85
11.	DISCONTINUATIONS	87
11.1.	Treatment Discontinuation.....	87
11.2.	Study Discontinuation	87
12.	EMERGENCY PROCEDURES	88
		
12.2.	Emergency Identification of Investigational Products	88
13.	REGULATORY CONSIDERATIONS.....	89
13.1.	Good Clinical Practice	89
13.2.	Investigator Responsibilities	89
13.3.	Subject Information and Informed Consent.....	90
13.4.	Confidentiality.....	90
13.5.	Protocol Amendments.....	90

LIST OF TABLES

Table 1:	Study Objectives.....	32
Table 2:	Study Endpoints	33
Table 3:	Table of Events.....	42
Table 4:	Dose Levels.....	57
Table 5:	Allowed Dose Reductions.....	61
Table 6:	Dose Adjustment Guidelines for CC-122 Related Non-hematologic Toxicities.....	62
Table 7:	Dose Adjustment Guidelines for CC-122 Related Hematologic Toxicities	65
Table 8:	Recommended Treatment Modification for Nivolumab	66
Table 9:	Confidence Interval for 20% and 35% Response Rate for Different Scenarios of Sample Size (Wilson Score Interval)	76
Table 10:	Abbreviations and Specialist Terms	101
Table 11:	Time Point Response: Subjects With Target (\pm Non-target) Disease	108
Table 12:	Time Point Response: Subjects With Non-target Disease Only	109
Table 13:	Child-Pugh Classification	119

LIST OF FIGURES

Figure 1:	Effect of CC-122 Combined with Nivolumab on IL-2 Secretion from SEB Stimulated PBMC.....	23
Figure 2:	Effects of CC-122 and Nivolumab in PBMC-mediated-Killing of JHH4 Cells	24
Figure 3:	Overall Study Design.....	36
		
Figure 5:	BCLC Staging and Treatment Schedule	118
Figure 6:	Diarrhea Management Guidelines	137

Table 2: Study Endpoints

Endpoint	Name	Description	Timeframe
Primary Phase 1	The incidence of dose limiting toxicities (DLTs) and the incidence and severity of treatment-emergent adverse events (TEAEs)	See Section 7.6 for the definition of DLTs	End of Phase 1
Primary Phase 2	Preliminary efficacy as measured by overall response rate (ORR)	The combined incidence of complete response (CR) + partial response (PR), by investigator assessment of response by Response Evaluation Criteria in Solid Tumors (RECIST) 1.1	End of Study

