6.5.1. Assessment of Response According to RECIST 1.1

Response assessments include computed tomography (CT) scan or magnetic resonance imaging (MRI). The regions to be imaged are the chest and abdomen/pelvis, as well as any other sites

required for tumor imaging. The same mode of imaging for lesion evaluation at screening must be used consistently throughout the study.

The CT imaging should include contrast unless medically contraindicated. Conventional CT should be performed with contiguous cuts of 5 mm or less in slice thickness. Spiral CT should be performed by use of a 5 mm contiguous reconstruction algorithm.

All subjects with evidence of objective tumor response (CR or PR) should have the response confirmed with repeat assessments at the next scheduled scan, but after no less than 4 weeks. Response assessments must have occurred ≥ 6 weeks from Cycle 1 Day 1 to be considered as stable disease (SD) for a best response.

Additional details and definitions of response are found in Appendix B in Section 18.2.

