4.2. Study Endpoints

Table 2: Study Endpoints

Endpoint	Name	Description	Timeframe
Primary Phase 1	The incidence of DLTs and the incidence and severity of treatment-emergent adverse events (TEAEs)	See Section 7.6 of protocol for the definition of DLTs	Dose Escalation Phase
Primary Phase 2	Preliminary efficacy as measured by ORR	The combined incidence of CR + PR, by investigator assessment of response by RECIST 1.1	Dose Escalation and Dose expansion Phase
Secondary	Preliminary efficacy	Disease control rate (DCR), duration of response (DoR), progression free survival (PFS), overall survival (OS), and time to progression (TTP) based on investigator assessment of response using RECIST 1.1 guidelines	Dose Escalation and Dose expansion Phase
Secondary	Plasma PK parameters	Including but not limited to maximum observed concentration (C_{max}), area under the concentration time curve (AUC), time to maximum concentration (T_{max}), terminal half-life ($t_{1/2}$), apparent total body clearance (CL/F) and apparent volume of distribution (V_z/F) for CC-122 and Nivolumab after multiple dose administration	Dose Escalation Phase
[REDACTED]	[REDACTED]	[REDACTED]	[REDACTED]
[REDACTED]	[REDACTED]	[REDACTED]	[REDACTED]
[REDACTED]	[REDACTED]	[REDACTED]	[REDACTED]

Endpoint	Name	Description	Timeframe
[REDACTED]	[REDACTED]		[REDACTED]

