10.3. Duration of Response (DoR) and duration of SD

DoR and duration of SD are derived for RECIST 1.1 and irRECIST separately and are defined as per the rules in Table 7.

Table 7: DoR and Duration of SD Derivation Rules

Endpoint	Derivation	Common Censoring Rules
DoR	
For subjects with an unconfirmed BOR of PR or CR:
 
DoR is measured from the date the criterion is first met for CR/PR (whichever is first recorded) until the first date when PD is documented or death occurred.
	
If the subject is still alive and did not experience PD at the date of cutoff, DoR and duration of SD will be censored at the date of last adequate¹ post-baseline tumor assessment prior to the cutoff date.
 
If a subject progresses or dies after an extended lost-to-follow up time (two or more missed assessments), DoR and duration of SD will be censored on the date of last adequate tumor assessment.

Duration of SD	
For subjects with an unconfirmed BOR of SD:
 
Duration of SD is measured from the first dose date (i.e. the first dose of CC-122 or Nivolumab whichever occurred first) until the first date when PD is documented or death occurred.
	

Abbreviations: BOR = best overall response; CR = complete response, SD = stable disease, PD = progressive disease, PR = partial response.

¹ Adequate tumor assessment is defined as the latest tumor assessment which is not missing or recorded as “not done” or “not all evaluable”.

The Kaplan-Meier estimate of median DoR and SD for both RECIST 1.1 and irRECIST along with a 2-sided 95% CI ([REDACTED]) will be provided by using Safety and EE Populations. The Kaplan-Meier estimate will only be provided for the phase and dose cohort/subgroup where the following conditions are met:

- DoR (RECIST 1.1): at least 3 subjects have unconfirmed DCR;
- DoR (irRECIST): at least 3 subjects have unconfirmed irDCR;
- Duration of SD (RECIST 1.1): at least 3 subjects with BOR of SD;

- Duration of SD (irRECIST): at least 3 subjects with irBOR of SD.

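### RECIST 1.1 ORR is derived both confirmed and unconfirmed with neither named as the main result, and DoR and time to response rest on unconfirmed responders only

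*SAP*

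**What the plan says.** **Endpoint.** Protocol Table 2 defines the Phase 2 primary endpoint as "The combined incidence of complete response (CR) + partial response (PR), by investigator assessment of response" under RECIST 1.1. SAP Table 2 has "The combined incidence of CR + PR, by investigator assessment of response by RECIST 1.1". Neither says whether the response must be confirmed.

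**Confirmation.** Protocol section 6.5.1: "All subjects with evidence of objective tumor response (CR or PR) should have the response confirmed with repeat assessments at the next scheduled scan", with a minimum gap of 4 weeks. SAP section 10.2: "Confirmation of response requires repeat assessment of response (CR or PR) at the next scheduled scan more than 4 weeks" after the first response. SAP Table 5 sets out the resulting best overall response (BOR); a PR followed by SD becomes SD.

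**ORR.** SAP section 10.2 says "Confirmed BOR will only be used to summarize ORR by RECIST1.1, with unconfirmed BOR used in the derivation of ORR" and continues the second list with DCR, DoR, PFS and TTP among others. Under the ORR and DCR heading it adds "Unconfirmed ORR, confirmed ORR, DCR and sustained DCR will be derived separately". Table 6 has one RECIST 1.1 ORR row for each version, and each receives a count, percentage and Clopper-Pearson interval.

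**DoR and time to response.** SAP Table 7 defines DoR "For subjects with an unconfirmed BOR of PR or CR". Section 10.4 times the first CR or PR from the unconfirmed BOR. Neither has a confirmed-responder version.

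**Changes from protocol.** SAP section 15 does not mention confirmation. It does say that the expansion phase will not take place and that the futility analysis is dropped.

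**The concern.** Two things follow from these rules.

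First, key efficacy analyses are run in the Safety and Efficacy Evaluable Populations (SAP section 5.2.6), so there are 2 × 2 = 4 RECIST 1.1 ORRs. The protocol summary settles the population, since it makes the Treated Population primary and SAP section 15 renames that the Safety Population. Nothing visible settles confirmation. In an open-label, single-arm, investigator-assessed study, the headline ORR could then be picked after the data are seen.

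Second, DoR is a stated rule applied to a set that the confirmed analysis does not recognise. If the report leads with confirmed ORR, the duration beside it belongs to a different and possibly larger group, which includes subjects whose response was seen on one scan only.

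**Working it through.** **1. The plan's own ORR figure.** Protocol Table 9 gives a Wilson 95% interval of 0.205 to 0.529 for 35% with n = 30. With z = 1.96:
- centre = (p + z²/2n)/(1 + z²/n) = (0.35 + 0.0640)/1.1281 = 0.3670
- half-width = z·√(p(1−p)/n + z²/4n²)/(1 + z²/n) = 1.96 × √(0.007583 + 0.001067)/1.1281 = 0.1616
- interval = 0.2054 to 0.5286, which agrees.

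The table does not say which kind of response it counts.

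**2. One subject, four endpoints.** SAP section 10.2 gives its own example of PR, SD, PD and calls the unconfirmed BOR a PR. Table 5 makes PR then SD a confirmed BOR of SD. So this subject is:
- a non-responder in confirmed ORR;
- a responder in unconfirmed ORR;
- in the DoR set, from the PR scan to the PD scan (two intervals, 16 weeks on the 8-week schedule);
- an event in time to response.

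A PR followed by PD at the next scan enters DoR at about 8 weeks. A PR with no later adequate scan, in a subject still alive at the cutoff, enters DoR censored at the response scan, that is, at about zero.

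**3. Size for ORR.** Protocol section 9.3 plans up to about 20 escalation subjects, so one subject is 1/20 = 5 points. With Clopper-Pearson limits:
- 4/20 = 20%, 0.057 to 0.437
- 5/20 = 25%, 0.087 to 0.491

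Protocol section 7.2.1 instead gives 20 to 30 subjects; at 30 the step is 1/30 = 3.3 points. SAP section 10 presents efficacy by dose cohort, and in a cohort of 6 the step is 1/6 = 16.7 points.

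**4. Range of non-confirmation (assumed; not in the documents).** If a share q of first responses is not confirmed, unconfirmed ORR = confirmed ORR/(1 − q). For a confirmed ORR of 20%:
- q = 0.10: 22.2%
- q = 0.20: 25.0%
- q = 0.30: 28.6%

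In 20 subjects with 4 confirmed responders, 4/(1 − q) is 4.4, 5.0 or 5.7. That is between none and two extra responders.

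**5. Direction for DoR (illustration only).** Suppose confirmed responders have exponential DoR with median m, and a share f of the set are one-scan responders who progress at the next 8-week scan (1.84 months). The median of the mixed set is m × log2(2(1 − f)), provided this exceeds 1.84 months.

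| m (months) | f = 0.10 | f = 0.20 | f = 0.30 |
|---|---|---|---|
| 6 | 5.1 | 4.1 | 2.9 |
| 12 | 10.2 | 8.1 | 5.8 |
| 18 | 15.3 | 12.2 | 8.7 |

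Both m and f are assumptions. The shift is usually downward, though a PR followed by long SD could have a long DoR.

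**The case against.** The strongest reply is that nothing is hidden. Confirmed ORR is fully prespecified and will always be tabulated with its own interval, in a labelled row beside the unconfirmed one. Read with Table 6, the sentence in section 10.2 is clumsy rather than contradictory: it describes two ORRs. The DoR set does match a reported numerator, the unconfirmed row. Listings of confirmed and unconfirmed BOR and of DoR would let someone derive the confirmed version. And with about 4 confirmed responders a Kaplan-Meier median is fragile. If one uncensored 8-week subject joins four uncensored confirmed responders with longer durations, the median moves only from the midpoint of the second and third confirmed durations to the second.

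Most of this stands, and it rules out several stronger readings:
- **That ORR is inflated.** Not shown. Only the unconfirmed row can exceed the confirmed one, and both are reported.
- **That the comparison with 20% is compromised.** In the original design it could have been: at n = 30, 11 responders give a Wilson lower limit of 0.219 and 10 give 0.192, on either side of 20%. But SAP section 15 cancels the expansion phase in which ORR was primary, together with the futility analysis, and the protocol summary calls all analyses descriptive.
- **That the DoR rule flatters the treatment.** It usually shortens the median.
- **That the irRECIST endpoints share the fault.** SAP Table 4 says confirmation is not mandatory for irCR, and irRECIST is exploratory.
- **That the protocol makes confirmation absolute.** Its word is should, although SAP Table 5 is headed as applying when confirmation is required.

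What the reply does not answer is that no visible text says which ORR is the main one, and that no confirmed-responder DoR is planned.

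**Conclusion.** The point holds as one of ambiguity in ORR and a mismatched set in DoR and time to response, for RECIST 1.1 only. It still matters after the cancellation because SAP Table 2 includes dose escalation in the timeframe for ORR and DoR, and section 5.2.6 keeps both as key analyses. ORR would be overstated only if the unconfirmed version were presented as the main result. In about 20 subjects, each unconfirmed responder is worth about 5 points of ORR and, beside four confirmed responders, one-fifth of the DoR set.

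This rests on the planned escalation size and on an illustrative 4 or 5 responders. The documents give no non-confirmation rate and no expected DoR, so no particular shift in median DoR can be claimed. That no main ORR is named applies to the visible text: protocol Appendix B, to which section 6.5.1 refers for response definitions, and some SAP text are not available.

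**What to change.** - **SAP section 10.2 and Table 6:** name confirmed RECIST 1.1 ORR in the Safety Population as the main ORR, and label unconfirmed ORR as supportive.
- **SAP Table 7 and section 10.4:** derive the main RECIST 1.1 DoR and time to response in confirmed responders, dated from the first scan that meets the criteria. Keep the unconfirmed versions as supportive. Restate the condition for a DoR Kaplan-Meier estimate, now at least 3 subjects with unconfirmed disease control, for the confirmed set.
- **irRECIST endpoints:** leave unchanged.
- **SAP section 15:** list any departure from the protocol's confirmation rule that is kept.

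The cost is a few sentences and one extra derivation from data already collected. The headline ORR may be lower, and fewer subjects will contribute to DoR.
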